### Tertiary Objective

The tertiary objective is to compare the above identified incident rates of adverse events per individual conventional systemic treatment in a dermatologist-verified adult atopic dermatitis (AD) patient population with the following two matched cohorts: The Danish background population AND Patients diagnosed with AD not receiving systemic therapies (see section 9.7).

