**Cohort entry (index date) for exposed:**

- 1) Date of initiation of the second administration/filled prescription of the conventional systemic therapy for AD,
- 2) Last inclusion date is December 31st, 2021, to allow for a minimum of one year of follow-up.

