### Treatment series

Treatment series are defined as periods of time in which a patient is considered on active treatment. The allowable gap between administrations of the same drug is 150 days to aggregate the treatment series. If the gap exceeds 150 days, patients are considered to have initiated a new treatment series. The allowable gap is based on the common gap of 90 days between each filled prescription, with an additional extension of 60 days to mirror the design of ORALSURV, which allowed for up to 2 months of discontinuation for safety issues.

The duration of active therapy following the last filled prescription or administration is set at 120 days, reflecting the standard 90-day prescription interval plus an additional 30 days, as outlined by Fleischmann et al. . Each treatment series is considered separately, as concomitant therapies were allowed in the ORALSURV study design.

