### Follow-up and exposure and censoring

Patients are followed from the index date until the earliest occurrence of one of the following: the event of interest, the study closing date (30 December 2022), initiation of a

biological therapy or JAK inhibitor, death, the development of a condition that would qualify for one of the treatments of interest (Table 1), or migration.

When using treatment series, exposure time is calculated and cumulated based on the specific therapy received. Except for the event of interest, any of the previously mentioned cases will result in censoring.

Additional analyses will be conducted on an intention-to-treat basis.

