## Events

During the treatment series, an adverse event can be adjudicated to the ongoing treatment. In the intention-to-treatment (ITT) study design, the event can be adjudicated to the treatment initiated at the index date.

If a patient is receiving overlapping treatments, any adverse event occurring during both therapies will be adjudicated to the therapy the patient has been on for the longest duration. Such events are referred to as overlapping events.

In the primary analyses, for overlapping events, the event is assigned to the drug the patient has been on the longest.

Multiple sensitivity analyses will be conducted to address overlapping events:

- The event is assigned to the most recent drug.
- The event is attributed to both drugs.
- The event is attributed to neither drug and the patient is censored.

Serious infections are defined as those requiring hospital admission for more than one day (Table V), and infections with HIV, hepatitis B or C, tuberculosis, or infections resulting in death.

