**Patient characteristics:**

Descriptive statistics will be presented to describe patient characteristics performed for all groups:

- a) dermatologist-verified adult patient population with atopic dermatitis (AD) receiving conventional systemic treatments as per inclusion/exclusion criteria,
- b) cohort-matched general Danish population
- c) cohort-matched patients with AD not receiving systemic treatment (see section above for matching criteria).

Categorical covariates will be described by frequency distribution while continuous covariates expressed in terms of their mean and standard deviation or median and interquartile range (IQR) as appropriate. The descriptive statistics will be captured in a statistical report with aggregated data in tables.

Between group comparisons for baseline characteristics:

Pearson's chi-square test will be used for dichotomous categorical variables, t-test will be used for continuous variables, and the Mann-Whitney U test for non-parametric variables. The statistical analysis will be captured in a statistical report with aggregated data in tables.

Primary endpoint statistical analysis:

Incidence rates of major adverse cardiovascular events (MACE) and malignancy (excluding non-melanoma skin cancer (NMSC)) will be presented per 10,000 person-years at risk with 95% confidence intervals. The incidence rates will be reported for each group separately: a) a dermatologist-verified adult patient population with atopic dermatitis (AD) receiving conventional systemic treatments as per inclusion/exclusion criteria, b) cohort-matched general Danish population and c) cohort-matched patients with AD not receiving systemic treatment (see section above for matching criteria). For group a, the incident rates will be presented per individual conventional systemic treatment (see table II).

In cases where patients received two systemic treatments or more during the data collection period, each treatment series will be analyzed independently. The statistical analysis will be captured in a statistical report with aggregated data in tables.

In the primary analyses, overlapping events will be attributed to the drug to which the patient has been exposed for the longest duration.

Secondary endpoint statistical analysis:

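### Crude rates for treated patients and matched comparators appear to cover different lengths of follow-up, so for outcomes that rise with age the comparator rates are likely too high relative to the treated rates

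*Protocol*

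**What the plan says.** All of the following is in the protocol.

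- **Treated person-time.** Section 8.7, Treatment series: "The allowable gap between administrations of the same drug is 150 days to aggregate the treatment series", and "The duration of active therapy following the last filled prescription or administration is set at 120 days". Follow-up and exposure and censoring: "When using treatment series, exposure time is calculated and cumulated based on the specific therapy received".
- **Treated events.** Section 8.7, Events: "During the treatment series, an adverse event can be adjudicated to the ongoing treatment".
- **End of follow-up.** One rule is given: "Patients are followed from the index date until the earliest occurrence of one of the following: the event of interest, the study closing date". That date is set at 30 December 2022, and the other stops are the start of a biologic or JAK inhibitor, death, a newly arising condition that could be treated with the study drugs, and migration. The end of a treatment series is not on the list.
- **Start of follow-up.** Section 8.2 has a heading "Cohort entry (index date) for exposed" and no counterpart for comparators. Index date is a candidate matching variable in section 8.7, but it is defined there by a prescription date, which a comparator does not have.
- **Matching.** Section 8.7 names baseline variables only: age, sex, index date and presence of a cardiovascular risk factor.
- **Reporting.** Section 8.7, primary and secondary endpoint analyses: "The incidence rates will be reported for each group separately", as rates per 10,000 person-years. The treated group is split by drug; the comparator groups appear to get one figure each. No standardisation is mentioned.
- **Comparison.** The tertiary objective in section 7 is to "compare the above identified incident rates of adverse events per individual conventional systemic treatment" with the two matched cohorts. The method is Cox regression, with no time scale given. Intention-to-treat analyses are additional.

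**The concern.** Matching makes the groups alike on the index date. It does not keep them alike if one group's clock stops when a course of treatment ends and the other's runs for years. The longer-followed group then contributes person-time at older ages and in later calendar years. MACE, malignancy and death rise with age, so the comparator rate is pushed up for a reason unrelated to the drug.

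The study is meant to put treated rates in context, and section 8.1 says that the design isolates the effect of treatment. A reader who sets the per-drug rate beside the comparator rate would be comparing unlike person-time, in a direction that can hide harm for both primary outcomes.

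**Working it through.** **1. The protocol's own figures.** Series rules: 90 + 60 = 150 days and 90 + 30 = 120 days, as stated. Expected MACE: 13,000 × 0.015 = 195 events a year, consistent with the stated figure of over 100. Neither bears on the point. The protocol gives no treatment duration, entry-date distribution or age gradient, so the size of the effect can only be shown under assumptions.

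**2. Longest possible windows.** Entry runs from 1 January 1995 to 31 December 2021 and follow-up ends in December 2022. A comparator can therefore contribute between about 1 and 28 years. A treated patient contributes the series plus the 120-day tail.

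**3. Simulation under no true difference in risk.** There were 400,000 people per group, with death as a competing exit. Treated time was 120 days plus an exponential length, capped at study end; comparator time ran to study end. Assumptions:
- mean entry age 35 or 45;
- entry uniform over 1995–2021 or 2010–2021;
- mean extra series length 0.5, 1, 2 or 4 years;
- event rate doubling every 8, 10 or 15 years of age (log-rate slopes ln 2/8 = 0.087, ln 2/10 = 0.069 and ln 2/15 = 0.046 per year), or no age trend.

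One case in full (entry 1995–2021, mean age 45, extra length 2 years, doubling every 10 years):
- Treated: mean follow-up 2.2 years, mean attained age 46.7, rate 39.6.
- Comparator: mean follow-up 12.7 years, mean attained age 51.9, rate 54.9 on the same scale.
- Ratio = 39.6 / 54.9 = 0.72.
- Cross-check from the age gap alone: 2^((46.7 − 51.9)/10) = 2^(−0.52) = 0.70.

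Crude rate ratio, treated over comparator, for a drug with no effect:

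| Entry | Mean age 35 | Mean age 45 |
|---|---|---|
| 1995–2021 | 0.51–0.78 | 0.62–0.82 |
| 2010–2021 | 0.67–0.91 | 0.84–0.94 |

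Across scenarios, mean follow-up was about 0.8–3.8 years treated against 6.6–13.7 years comparator, and treated person-time was 1.3–7.9 years younger. With no age trend the ratio was 0.96–1.03. A true ratio of 2 appeared as about 0.94–1.92 for age-dependent outcomes. Ending comparator time with the matched patient's treated time brought the null ratio back to about 1.0 (0.92–1.13, simulation noise).

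**4. Simpler check without death or other exits.** Take a hazard proportional to exp(g·t), potential follow-up uniform on 1 to 28 years (mean 14.5), and treated time exponential with mean m, capped by study end. Each group's rate is ∫S(t)exp(g·t)dt / ∫S(t)dt, where S(t) is the fraction still contributing time at t.

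| g | m = 1 | m = 2 | m = 3 |
|---|---|---|---|
| 0.05 | 0.62 | 0.65 | 0.68 |
| 0.07 | 0.50 | 0.53 | 0.57 |
| 0.09 | 0.39 | 0.43 | 0.47 |

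For g = 0.07 and m = 2, the ratio is 1.149 / 2.156 = 0.53. These values exaggerate, because death and the other listed exits would shorten comparator time.

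**5. What truncating comparator time would cost.** Under the inputs of step 4, mean comparator follow-up falls from 14.5 years to 0.99 (m = 1) or 2.76 (m = 3). The loss of person-years is 1 − 0.99/14.5 = 93% or 1 − 2.76/14.5 = 81%. Comparator events fall by 87–97%. The log-scale interval widens by the square root of the ratio of event counts, about 2.8 to 6.1 times.

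**The case against.** The strongest reply has four parts.

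- **The protocol never says that comparators are followed to the end of 2022.** That stands. It is inferred from the single rule given, and an analysis plan could yet tie comparator time to the matched series. But the protocol itself fixes the treated exposure rule, the follow-up rule and the three-group display, and followed as written they give unequal windows.
- **The primary and secondary objectives are to quantify rates in treated patients, and those rates are untouched.** That also stands. The weakness lies in the comparator rates printed beside them.
- **The formal comparison is by Cox regression, and no ratio of crude rates is planned.** This largely stands. On time since index, each event is compared with people equally far from index, which removes most of the age drift, and intention-to-treat gives both groups the same window. But the time scale is not stated, cumulating treated time across gaps would break the alignment, and Cox regression does not correct the rate tables. Propensity matching and weighting balance baseline only, and rates by calendar period do not equalise attained age.
- **The size is assumption-driven.** True. Longer series, later entry and repeat series after a gap all move the ratio towards 1.

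A reader might infer that the plan makes every drug look safe. The documents do not support that. Outcomes with little age trend are hardly affected, events clustered soon after index could bias the other way, and a true doubling still shows above 1 in most scenarios.

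**Conclusion.** The point holds for the side-by-side crude rates of age-dependent outcomes, which include both primary outcomes. It rests on reading the general follow-up rule as applying to comparators. If it does not apply to them, the protocol gives them no end date, and that needs correcting too.

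With death allowed for, the null rate ratio is roughly 0.5 to 0.94 over the assumed entry dates, durations and gradients, and about 1.0 without an age trend. The direction for age-rising outcomes was the same in every scenario; the size cannot be settled from the protocol. Because the treated rates themselves are sound and the tertiary comparison can be protected by its time scale, this is a should-fix.

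**What to change.** 1. Assign each comparator the index date of its matched patient, and state when comparator follow-up ends.
2. Report rates for the general-population and untreated AD groups per drug-matched set, standardised to the treated person-time by attained age, sex and calendar period.
3. State that the Cox model runs on time since index, with treated time not joined across gaps between series.
4. Add a sensitivity analysis in which comparator time ends with the matched patient's series. Say which series applies, and how a comparator reused under matching with replacement gets an end date for each match.

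**Cost.** Items 1 to 3 need wording and a little more analysis work, and discard no data. Item 4 gives markedly wider comparator intervals (about 2.8 to 6.1 times on the log scale under the inputs above), which is why standardisation should be the main analysis and truncation the sensitivity analysis.

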## Events

During the treatment series, an adverse event can be adjudicated to the ongoing treatment. In the intention-to-treatment (ITT) study design, the event can be adjudicated to the treatment initiated at the index date.

If a patient is receiving overlapping treatments, any adverse event occurring during both therapies will be adjudicated to the therapy the patient has been on for the longest duration. Such events are referred to as overlapping events.

In the primary analyses, for overlapping events, the event is assigned to the drug the patient has been on the longest.

Multiple sensitivity analyses will be conducted to address overlapping events:

- The event is assigned to the most recent drug.
- The event is attributed to both drugs.
- The event is attributed to neither drug and the patient is censored.

Serious infections are defined as those requiring hospital admission for more than one day (Table V), and infections with HIV, hepatitis B or C, tuberculosis, or infections resulting in death.

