**Exclusion criteria rationale:**

The aim is to ensure that the adverse events registered cannot be attributed to any current or previous cases of cancer (criteria 1), other treatments (criteria 2 and 3), or other inflammatory diseases and their treatments (criteria 4). Additionally, it ensures that systemic treatments are administered specifically for AD and not for any other condition (criteria 4).

Given the high number of AD patients in the registry combined with previous experience each treatment group it is expected to comprise around 1000 patients for the majority of treatments.

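### The primary per-drug malignancy rate uses the same unlagged on-treatment window as the acute outcomes, and no planned analysis allows for cancer latency

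*Protocol*

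**What the plan says.** **Start of risk time.** Section 8.2 sets the index date for exposed patients as "Date of initiation of the second administration/filled prescription of the conventional systemic therapy for AD". Section 8.7 (Follow-up and exposure and censoring) adds: "Patients are followed from the index date until the earliest occurrence of one of the following". No lag follows the index date for any outcome.

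**End of risk time.** Section 8.7 (Treatment series) states: "The duration of active therapy following the last filled prescription or administration is set at 120 days". The only reason given is "reflecting the standard 90-day prescription interval plus an additional 30 days". Gaps of up to 150 days are bridged within a series.

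**Attribution.** Section 8.7 (Events) states: "During the treatment series, an adverse event can be adjudicated to the ongoing treatment". Exposure time is accumulated by drug.

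**Which analysis is primary.** No single sentence says that the primary rate is on-treatment, and the list of events that end follow-up does not include the end of a series. It is inferred from three points in section 8.7. The primary endpoint text analyses each treatment series separately. The primary overlap rule allocates events that happen while two drugs are being taken. The alternative is described as extra: "Additional analyses will be conducted on an intention-to-treat basis".

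**Outcome and exclusions.** Table III makes malignancy excluding NMSC co-primary, and NMSC is a secondary endpoint. Section 8.2.2 excludes patients with recorded cancer other than NMSC before inclusion. Section 8.2 gives the purpose: "The aim is to ensure that the adverse events registered cannot be attributed to any current or previous cases of cancer".

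**The concern.** A window built from prescription intervals suits infections, zoster and thromboembolic events. It does not suit cancer, where disease can precede diagnosis by a long time and a drug effect may appear long after exposure.

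- **Early error.** The exclusion removes recorded cancers, not undiagnosed ones. A cancer diagnosed weeks after the second fill is charged to the drug, which works against the purpose stated for the exclusion. Section 8.9 concedes that drugs such as prednisolone may have been prescribed for something other than atopic dermatitis, so some prescribing for early symptoms of an undiagnosed cancer is possible.
- **Late error.** A cancer diagnosed more than 120 days after the last fill, or between two series of the same drug, belongs to no drug in the primary rate.

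Malignancy is half of the primary objective, and section 8.1 presents the matched comparison as isolating the effect of treatment. A per-drug cancer rate exposed to both errors cannot carry that reading.

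**Working it through.** **Inputs.** From section 8.7 (Treatment series): 90-day prescription interval, 120-day tail, 150-day gap. From section 8.2: index date at the second fill. The protocol gives no treatment durations, cancer rates, effect sizes or lags, so those below are assumptions.

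**1. The plan's own figures.** 90 + 30 = 120 days and 90 + 60 = 150 days. Both reproduce, and neither is derived from cancer latency.

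**2. Window by number of fills.** For k fills 90 days apart, the window from index is (k − 2) × 90 + 120 days.

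| Fills | Window (days) | Share in first 180 days | Share in first 365 days |
|---|---|---|---|
| 2 | 120 | 100% | 100% |
| 4 | 300 | 60% | 100% |
| 8 | 660 | 27% | 55% |

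**3. Each error alone, under assumed durations.** Let time from index to last fill be exponential with mean m years, followed by the tail c = 120/365.25 = 0.3285 year, in one uninterrupted course with a constant background rate. The share of on-treatment person-time in the first L years (L > c) is [c + m(1 − exp(−(L − c)/m))] / (m + c). Write S6 and S12 for L = 0.5 and L = 1.

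- Early error: no drug effect, but cancer detection doubled in the first 6 months. Apparent ratio = 1 + S6.
- Late error: true ratio 1.5 from month 12 onward. Apparent ratio = 1 + 0.5 × (1 − S12).

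| m (years) | S6 | S12 | Early error alone (truth 1.0) | Late error alone (truth 1.5) |
|---|---|---|---|---|
| 0.5 | 57% | 84% | 1.57 | 1.08 |
| 1 | 37% | 62% | 1.37 | 1.19 |
| 2 | 21% | 39% | 1.21 | 1.31 |
| 3 | 15% | 28% | 1.15 | 1.36 |

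Under the late-error assumption, unlagged ITT follow-up over 10 years gives 1 + 0.5 × 0.9 = 1.45. Over the same values of m, the on-treatment window observes about 1% to 25% of the time between years 1 and 10 after index.

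**4. Both errors together.** Take m = 1, so S6 = 0.366 and 0.5 × (1 − S12) = 0.192. With detection doubled early, the ratio is 1 + 0.366 + 0.192 = 1.56, above the assumed 1.5. With detection raised by half, it is 1 + 0.5 × 0.366 + 0.192 = 1.38, below it. The sign of the net error depends on inputs that the protocol does not give.

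**5. Does another planned analysis cover this?** ITT attributes events to the drug started at index, so it counts later cancers, but it starts at the same unlagged date. The listed sensitivity analyses (one use of a drug, overlap rules, calendar periods, inverse probability weighting) neither lag nor extend the cancer window. Starting at the second fill gives about 90 days after the first at the usual interval. That delay is not fixed and is not a cancer lag, and the one-use analysis would presumably remove it.

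**The case against.** Much of the case on the other side stands.

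- **ITT is already planned.** A reader might infer that the study misses late cancers altogether. It does not: the late error concerns the on-treatment rate only. ITT leaves the early error in place.
- **One year of follow-up.** A reader might infer that the last inclusion date, chosen "to allow for a minimum of one year of follow-up", is a promise broken by a 120-day window. It is not. That phrase concerns calendar time to study close, and the protocol treats follow-up and exposure time separately.
- **Existing cancers.** A reader might infer that known cancers are counted. Recorded prior cancers other than NMSC are excluded, so only those undiagnosed at index are at issue.
- **False reassurance.** A reader might infer that the rate is diluted towards no effect. If hazard doubles permanently from year 1 and duration is exponential, the share of person-time beyond 1 year is exp(−1/m). That gives ratios of about 1.14, 1.37 and 1.61 for means of 0.5, 1 and 2 years, against 2.0. But this model assumes the doubling, uses a single course, omits the 120-day tail and ignores the early error. The documents support no net direction.
- **Making ITT primary.** This is a debatable trade. ITT credits the index drug with cancers arising during later use of another conventional drug, since such switching does not censor. It would also leave the MACE-and-malignancy composite in section 8.1 without a common window.
- **The study is descriptive, and a SAP may add detail.** A descriptive per-drug rate still needs a window that fits its outcome. The protocol itself fixes this window and lists the sensitivity analyses.

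**Conclusion.** The point stands in limited form. By inference from section 8.7, the primary per-drug malignancy rate uses an unlagged window that ends 120 days after the last fill. It counts cancers undiagnosed at index and omits those found after a series ends. ITT repairs the second fault outside the primary rate. Nothing planned repairs the first.

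The firm figures are the windows: 120 days for two fills, and 300 days for four fills at the usual interval, all inside the first year. The ratios of 1.15 to 1.57 (early error, truth 1.0) and 1.08 to 1.36 (late error, truth 1.5) show that either error could matter. They rest on assumed durations and effects and are not estimates of the bias in this study. Its net direction and size cannot be derived from the documents.

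**What to change.** 1. State in section 8.7 that the primary per-drug rate is on-treatment, if that is intended.
2. For malignancy excluding NMSC and for NMSC, prespecify a lagged analysis. Risk time and event counting start 12 months after index (6 months as a sensitivity analysis) and use the planned ITT follow-up past the end of treatment. Both comparator cohorts get the same lag from the matched index date.
3. Report it beside the on-treatment rate, and do not base conclusions about drug-related cancer risk on the unlagged on-treatment rate alone.
4. Keep the treatment-series window for MACE, for the section 8.1 composite and for the acute outcomes.

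**Cost.** Protocol wording and a changed start date in the code, with no new data. The lagged analysis loses first-year events and person-time. Its later follow-up includes time on other conventional drugs, which should be stated when it is interpreted.

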To evaluate the robustness of the method applied to handle overlapping events in the primary analysis, multiple sensitivity analyses will be performed, in which overlapping events will alternatively be assigned to (a) the most recently administered drug, (b) attributed to both drugs, or (c) excluded by censoring the patient at the time of the event. These results will be presented separately.

Furthermore, a sensitivity analyses will be conducted reporting incidence rates for the years 1995-2001, 2002-2008, 2009-2015, and 2016-2022.

As a sensitivity analyses, a cox regression model with inverse Probability Treatment Weighting will be conducted.

Analyses will be conducted using SAS 9.4, Python v3.11.5, and R v4.4.1

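### Primary per-drug rates: an overlapping event goes only to the longest-used drug, while overlap person-time, on the natural reading, counts for both drugs, so the shorter-used drug's rate is understated

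*Protocol*

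**What the plan says.** All of the relevant text is in Section 8.7 of the protocol.

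- **Events (numerator).** Under Events, for a patient on overlapping treatments, "any adverse event occurring during both therapies will be adjudicated to the therapy the patient has been on for the longest duration". The same section restates this as the primary rule: "for overlapping events, the event is assigned to the drug the patient has been on the longest". The primary, secondary and tertiary analysis paragraphs repeat it.
- **Person-time (denominator).** Under Follow-up and exposure and censoring: "When using treatment series, exposure time is calculated and cumulated based on the specific therapy received". Under Treatment series: "Each treatment series is considered separately, as concomitant therapies were allowed in the ORALSURV study design". Under the primary endpoint analysis: "In cases where patients received two systemic treatments or more during the data collection period, each treatment series will be analyzed independently".
- **Reporting unit.** Rates in the treated cohort are given for each systemic drug separately, per 10,000 person-years with 95% confidence intervals.
- **Length of a series.** A drug is treated as active for 120 days after its last fill or administration.
- **Sensitivity rules for overlapping events.** The event goes to (a) the most recent drug or (b) both drugs, or it is (c) "excluded by censoring the patient at the time of the event".

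No sentence says what happens to the days on which two drugs run together.

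**The concern.** A rate is interpretable only if every day in the denominator could have contributed an event to the numerator. Here the event rule picks one drug, while the person-time text describes separate, complete series for each drug. Taken together, the overlap days of the shorter-used drug are counted as time at risk, yet any event on those days is recorded under the other drug.

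The primary objective is a rate for each drug, so the mismatch falls on the headline result and runs in one direction: a drug added to a longer-used one, or started in its tail, appears to have fewer events than it has. The tertiary Cox comparisons with the two matched cohorts use the same attribution, so on this reading they inherit it.

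**Working it through.** **Inputs.** The event rule and the person-time text are as set out above. The protocol gives no overlap share, so f is an assumption shown over a range. For illustration I use a true rate of 150 per 10,000 person-years, the annual MACE rate of 1.5% that Section 8.2 expects in AD populations (0.015 × 10,000 = 150). It is assumed the same for both drugs, in and out of overlap. The protocol states no per-drug rate, so there is no figure of its own to reproduce.

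**Step 1: the shorter-used drug under the primary rule.** Let its person-time be T, its hazard L, and f the share of T that overlaps a longer-used drug.

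- Events credited: L × T × (1 − f)
- Denominator: T
- Reported rate: L × (1 − f)

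The longer-used drug keeps both its overlap events and its overlap time, so its rate stays at L.

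| f | Shorter-used drug | Longer-used drug | Apparent ratio |
|---|---|---|---|
| 0.05 | 142.5 | 150 | 0.95 |
| 0.10 | 135 | 150 | 0.90 |
| 0.20 | 120 | 150 | 0.80 |
| 0.30 | 105 | 150 | 0.70 |
| 0.50 | 75 | 150 | 0.50 |

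**Step 2: the planned rules compared.** Take 1,000 person-years per drug and f = 0.2 for each. Each drug has 15 true events (0.015 × 1,000), 3 of them in overlap (15 × 0.2). Removing the 3 events but not the time gives 12 / 1,000 = 120 per 10,000.

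| Rule | Longer-used (older) drug | Shorter-used (newer) drug |
|---|---|---|
| Primary: longest-used drug | 150 | 120 |
| (a) most recent drug | 120 | 150 |
| (b) both drugs | 150 | 150 |
| (c) neither, censor at the event | 120 | 120 |

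Rule (a) moves the mismatch to the older drug. Rule (c) lowers both rates, because overlap time before the event stays in. Only (b) matches the denominators.

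**Step 3: matching time to events.** If the longest-duration rule is kept and the 200 overlap person-years leave the other drug's denominator, that drug's rate is 12 / 800 = 150 per 10,000. In general, L(1 − f) / (1 − f) = L.

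A simulation of 400,000 patients with 56% overlap agrees with the algebra. The shorter-used drug showed 67 per 10,000 under the primary rule (formula: 150 × 0.44 = 66), 152 with events counted for both drugs, and 153 with overlap time removed.

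**Step 4: can overlap arise without deliberate co-medication?** Yes. The 120-day tail of the old drug can run into the new drug's series at a switch. For a 365-day course of the new drug:

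- 30 days of overlap: f = 30/365 = 0.08, rate about 138 instead of 150
- 120 days of overlap: f = 120/365 = 0.33, rate about 101 instead of 150

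Cohort entry at the second fill (Section 8.2) may shorten this overlap.

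**The case against.** The strongest objection is that the double-counted denominator is inferred. The protocol says how exposure is accumulated in general and is silent on days with two drugs. A programmer who gave overlap days to the same drug as the event would contradict no sentence, and such detail is often left to an analysis plan. It stands that the point rests on reading three statements together, and a reader should not infer that the protocol says outright that overlap time is counted twice. It does not dispose of the point: the protocol itself fixes the event rule and describes how time accrues, and the text followed as written leads to the mismatch.

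Second, attribution to both drugs is already planned and would be presented separately, so the effect of the allocation rule would be visible. The additional intention-to-treat analyses credit events to the treatment begun at index and do not appear to use the longest-duration rule. Both are fair points, but neither corrects the headline primary rates or the tertiary comparisons.

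Third, several stronger readings are tempting and lack support:

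- That every drug's primary rate is biased. With equal hazards, the longest-used drug's rate is unchanged.
- That a particular drug, for instance prednisolone, would look safer. The documents list it among five study drugs and do not say which drug is usually the longer-running one.
- That the bias is large. Nothing in the documents excludes a small f.
- That combination exposure must be a separate category. This would alter the per-drug reporting, and Section 8.7 already foresees groups with too few patients or events.

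**Conclusion.** The point holds in this form. The single-drug event rule is explicit, and on the natural reading of the person-time text the shorter-used drug's primary rate is understated by the factor (1 − f). This assumes a constant hazard that is the same in and out of overlap, and overlap days counted in full for both drugs. The direction follows from the rules. The size cannot be derived from the documents, because no overlap share is given.

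Differences between the primary result and the sensitivity results under (a) and (c) would partly reflect unmatched accounting, so they are a weak test of robustness. If the sponsor intends overlap days to follow the event, the mismatch disappears, but the protocol has to say so.

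**What to change.** State in Section 8.7 that overlap person-time is allocated by the same rule as the overlapping event, in one of two ways:

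1. Make attribution to both drugs the primary rule, with overlap time counted for both. It is already programmed for as rule (b) and needs no change to the denominators described.
2. Keep the longest-duration rule and remove overlap days from the other drug's denominator. Mirror this for rule (a), removing them from the older drug.

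For rule (c), exclude overlap person-time for both drugs along with the overlapping events. Carry the chosen rule into the tertiary Cox comparisons.

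The cost is wording and some programming, with no new data. Option 1 counts some events under two drugs, so per-drug events cannot be summed. Option 2 leaves slightly less person-time for some drugs. A separate row for combination exposure is optional.
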